### 6.2.5. Date of Last Participation in the Trial

A subject's date of last participation in the trial is the last date of contact that the subject has with the trial and is recorded as the date of completion or date of withdrawal on the completion page of the CRF.

## Statistical Analysis Plan

### 6.2.6. Follow-up Phase

The follow-up phase covers the whole time that a subject is in the trial between Trial Day 1 and their date of last participation in the trial.

$$\text{follow-up duration} = (\text{last participation date}) - (\text{date of Trial Day 1}) + 1$$

### 6.2.7. On-treatment and Off-treatment Period

Subjects discontinuing the trial medication were encouraged to continue in the trial to provide all scheduled measurements. This will result in some subjects having information recorded both while taking trial medication and after trial medication has been discontinued.

The following definition of “on-treatment” and “off-treatment” periods are applied:

#### For Safety data:

- On-treatment period: period of time while the subject is on trial medication; it starts with the first intake of trial medication after randomization and ends 28 days after the last trial medication intake.

All safety analyses will be conducted considering the measurements and AEs observed during the on-treatment period (excluding MTT-emergent AEs [MEAEs]).

#### For Efficacy data:

- On-treatment period: period of time while the subject is on trial medication; it starts with the first intake of trial medication after randomization and ends 7 days after the last trial medication intake.
- Off-treatment period: period of time while the subject is not on trial medication; it starts the eighth day after the last trial medication intake and ends on the date of last participation in the trial.

All efficacy analyses will be conducted considering all measurements collected (i.e. including both on-treatment and off-treatment period data).

In addition, for the primary endpoint, supportive analyses will be conducted considering only measurements collected during the on-treatment period.

## Statistical Analysis Plan

### 6.3. MISSING DATA

Missing or partial dates will be resolved in the most conservative manner. Additional details regarding partial or missing dates for the different safety data are given in Sections 6.2.1, 7 and 9 where applicable.

Details of imputation of missing values for efficacy endpoints are given in Section 8. Subjects who discontinue trial medication should remain in the trial and continue to provide all scheduled measurements. While all efforts will be made to ensure subjects remain in the trial, the following planned imputation strategy will allow for appropriate analyses of FEV1, FVC, ease of expectoration VAS score, and CFQ-R respiratory domain in the presence of missing data.

To calculate baseline values, missing Visit 1 measurements will be replaced by Visit 0 (screening) measurements, if available.

Missing post-baseline measurements as a result of withdrawal from the trial will be imputed in both ITT and PP analyses using an imputation using dropout reason (IUDR) methodology. For subjects who withdraw from the trial due to AE, death, physician decision, or lack of efficacy, missing post-baseline measures as a result of withdrawal from the trial will be imputed using the baseline measurement (baseline observation carried forward [BOCF] procedure). Missing measurements as a result of other causes of withdrawal from the trial (i.e. lost to follow-up, relocation, pregnancy, major protocol deviation, sponsor decision, withdrawal of consent, or other) will not be imputed. Missing data at intermediate visits (i.e. where data is available at a later visit) will not be imputed. Any measurements excluded from the PP analysis at the BDRM, and any derived variables based on these excluded measurements, will be treated as missing data but will not be included in the imputation process.

Imputation of missing FEV1 measurements by means of BOCF is a reasonable assumption in studies of adult subjects with CF, as those subjects who withdraw from the trial will no longer receive trial medication and are thus likely to promptly return to their baseline lung function. Imputation by BOCF specifically inhibits any assumed prolongation of an observed early trial medication benefit implicitly conferred by a mixed model.

A framework of imputation by BOCF in combination with the IUDR strategy seeks to specifically address the primary question of interest, that is to provide a reliable estimation of the treatment group effect over 26 weeks as observed in all randomized subjects.

For time to first PDPE, subjects who do not have a PDPE during the trial will be censored at the date of last participation in the trial.

## Statistical Analysis Plan

For rate of PDPE, if a subject withdraws from the trial before Week 14 with no observed instances of a PDPE the number of PDPEs will be imputed using half the subject's historical (previous 12 months) PE count (rounded upwards) and their follow-up duration will be imputed as 26 weeks. If a subject withdraws from the trial after Week 14 with no observed instances of a PDPE the number of PDPEs will be imputed using one quarter the subject's historical (previous 12 months) PE count (rounded upwards) and their follow-up duration will be imputed as 26 weeks.

For the secondary efficacy analyses of number of days on antibiotics due to PDPE, number of days in hospital due to PDPE, and incidence of PDPEs, no imputation of missing data will be performed.

Imputed data will not be displayed in data listings unless otherwise specified.

### 6.4. VISIT WINDOWS

All ITT analyses will be performed using the visit as recorded on the CRF. In the case where a subject performed the IMP discontinuation visit, the following visit windows will be used to assign this visit to the most appropriate visit number for the purposes of analysis:

**Table 4: Visit windows for assigning IMP discontinuation visits to visit numbers**

Visit	Target Trial Day	Window
Visit 1 (Baseline)	1	≤Treatment Day 1
Visit 2 (Week 6)	43	Day 14 - Day 70
Visit 3 (Week 14)	99	Day 71 - Day 140
Visit 4 (Week 26)	183	Day 141 - Day 211

If this re-assignment of the IMP discontinuation visit to a visit number results in two spirometry assessments being available for the same visit then the following rules for selecting which assessment to use in the analysis will be used:

- If one assessment is recorded during the on-treatment period and the other is recorded during the off-treatment period, the assessment recorded during the on-treatment period will be used.
- Otherwise, if both assessments are recorded during the on-treatment period or both are recorded during the off-treatment period then, the one closest to the planned or scheduled visit date will be used. If the two observations are equidistant from the target day the one after the target day will be used in the analysis.

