#### 8.1. PRIMARY EFFICACY ENDPOINT AND ANALYSIS

The primary endpoint is the absolute change from baseline FEV1 (L) over the 26-week treatment period (measured at Weeks 6, 14 and 26). The primary analysis will include assessments as specified up until the time of last participation for each subject, including those performed off trial medication. For subjects who have an IMP discontinuation visit, the spirometry assessment done at this visit can be used instead of the assessment performed at the scheduled visit in line with the rules defined in Section 6.4.

In order to assess the potential impact of missing data on the results, sensitivity analyses will be performed (see Section 8.1.2 for more details):

- Pattern Mixture Model.
- Tipping Point Analysis.
- Mixed model repeated measures (MMRM) without imputation.
- Responder Analysis.

The following supportive analyses will also be performed:

- Using the PP set.
- Absolute change from baseline FEV1 (L) at 26 weeks and at 6 and 14 weeks.
- Absolute change from baseline percent predicted FEV1 (%) over 26 weeks.
- Relative change from baseline FEV1 (L) over 26 weeks.
- Relative change from baseline percent predicted FEV1 (%) over 26 weeks.

In addition, the following supportive analyses on the absolute change from baseline FEV1 (L) over the 26 week treatment period will be conducted based on on-treatment period data only:

Pharmaxis Ltd

DPM-CF-303

Final v1.0

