### Missing Data:

The analysis will use spirometry data which are consistent with the visit assignment as described in Section 6.4. Subjects who discontinue trial medication should remain in the trial and continue to provide all scheduled FEV1 measurements. The primary analysis will include all available on-treatment and off-treatment period data, regardless of adherence to or discontinuation of trial medication. While all efforts will be made to ensure subjects remain in the trial, the following planned imputation strategy will allow for an appropriate primary analysis in the presence of missing FEV1 data.

To calculate baseline values, missing Visit 1 measurements for the primary efficacy variable (FEV1) will be imputed using Visit 0 (screening) measurements, if available.

Missing post-baseline measurements as a result of withdrawal from the trial for the primary efficacy variable (FEV1) will be imputed using an IUDR methodology. For subjects who withdraw from the trial due to AE, death, physician decision, or lack of efficacy, missing post-baseline FEV1 measures as a result of withdrawal from the trial will be imputed using the baseline FEV1 measurement (BOCF procedure). Missing FEV1 measurements as a result of withdrawal from the trial, where the withdrawal was as a result of other causes (i.e. lost to follow-up, relocation, pregnancy, major protocol deviation, sponsor decision, withdrawal of consent, or other) will not be imputed. Missing data at intermediate visits (i.e. where data is available at a later visit) will not be imputed.

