## Statistical Analysis Plan

Imputation of missing FEV1 measurements by means of BOCF is a reasonable assumption in studies of adult subjects with cystic fibrosis, as those subjects who discontinue will no longer receive treatment and are thus likely to promptly return to their baseline lung function. Imputation by BOCF specifically inhibits any possible prolongation of an observed early treatment benefit implicitly conferred by a mixed model. Considering the higher drop-out rate observed with the experimental treatment compared to control in previous studies (DPM-CF-301 and DPM-CF-302), BOCF is not likely to favour the mannitol arm.

The primary analysis will target the de facto estimand assessing the effect of a treatment policy (Estimand 1 in Mallinckrodt ) by:

- Including all available on-treatment and off-treatment period data.
- Handling missing data based on a clinically reasonable assumption not biased in favor of the mannitol arm.

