### 8.1.2. Sensitivity Analyses of the Primary Endpoint

To elicit insights into the effect of imputation via the planned BOCF+IUDR framework, the following sensitivity analyses of the primary endpoint will be conducted:

- Sensitivity Analysis 1: Pattern Mixture Model.
- Sensitivity Analysis 2: Tipping Point Analysis.
- Sensitivity Analysis 3: MMRM without imputation.
- Sensitivity Analysis 4: Responder Analysis.

As for the primary analysis, these sensitivity analyses target the de facto estimand assessing the effect of a treatment policy. These analyses will include all available on-treatment and off-treatment period data, regardless of adherence to or discontinuation of trial medication.

Planned approaches for handling missing data in Sensitivity analyses 1, 2, and 4 are not likely to favor the experimental arm (for more details see specific sections below.)

In the first 3 analyses, the mean absolute change from baseline FEV1 (L) over 26 weeks (including assessments at Weeks 6, 14 and 26) and at each post-baseline visit will be compared between the two treatment groups. For the responder analysis, the comparison between treatment groups will be performed at Week 26 (however subjects who withdraw from the trial earlier are assumed to be non-responders).

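### The SAP's rule for choosing between two spirometry values can replace an observed off-treatment FEV1 with an earlier on-treatment one, contrary to the treatment-policy estimand of the primary analysis

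*SAP*

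**What the plan says.** Under Table 4 in SAP 6.4, a discontinuation visit is mapped to Visit 2 (Days 14-70), Visit 3 (Days 71-140) or Visit 4 (Days 141-211). Two rules settle the case where this puts two spirometry assessments in one slot. The first is that if one is on-treatment and "the other is recorded during the off-treatment period, the assessment recorded during the on-treatment period will be used". The second, for two values of the same status, takes the one nearest the target day. For efficacy, SAP 6.2.7 says the on-treatment period "ends 7 days after the last trial medication intake".

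The rule reaches the primary analysis openly. SAP 8.1 says that "the spirometry assessment done at this visit can be used instead of the assessment performed at the scheduled visit", and the missing-data text in 8.1.1 begins: "The analysis will use spirometry data which are consistent with the visit assignment as described in Section 6.4".

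The SAP also makes these commitments:
- 6.2.7: "All efficacy analyses will be conducted considering all measurements collected (i.e. including both on-treatment and off-treatment period data".
- 8.1.1: "The primary analysis will include all available on-treatment and off-treatment period data, regardless of adherence to or discontinuation of trial medication".
- 8.1.1: "The primary analysis will target the de facto estimand assessing the effect of a treatment policy".
- 8.1.2: "As for the primary analysis, these sensitivity analyses target the de facto estimand assessing the effect of a treatment policy".

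**The concern.** Under a treatment policy, the outcome of interest is FEV1 at the scheduled time whether or not the subject is still taking drug. Subjects who stop drug and stay in the trial are the ones who separate that estimand from an on-treatment one. The first rule chooses between two observed values by treatment status, and so sets aside the off-treatment value for some of these subjects.

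The effect could go either way. It would favour mannitol if benefit still present within 7 days of the last dose has gone by the scheduled visit. It would be nil if FEV1 returns to baseline as promptly as SAP 8.1.1 supposes. It could reverse if FEV1 is depressed around the time of stopping, or if later therapy raises it, a possibility that SAP 8.1.3.4 recognises.

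Nothing in the plan would reveal the effect. Sensitivity Analyses 1-4 vary the handling of missing data or the definition of response, and none is described as lifting the rule. FVC uses the same rule. The responder analysis reads Week 26 only, so one substitution can decide a subject's status.

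**Working it through.** **When the rule overrides a scheduled value.** Four conditions must hold together:
1. The discontinuation visit is no more than 7 days after the last dose (SAP 6.2.7).
2. It falls in a post-baseline Table 4 window.
3. A scheduled visit has spirometry in the same slot.
4. That scheduled visit is more than 7 days after the last dose.

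Protocol 9.2 asks for the discontinuation visit within 2 weeks of the last dose and for scheduled visits to continue, so all four can occur. Example: last dose Day 20, discontinuation visit Day 24, Visit 2 on Day 43. The Day 24 value is analysed as Week 6 and the on-target Day 43 value is dropped.

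**How far apart the values can be.** With Visit 4 on target, 183 - 141 = 42 days. With Visit 4 at +28 days (Protocol 8.1.2.11), 211 - 141 = 70 days.

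**How many date combinations are affected.** Take last-dose Days 1-182, a discontinuation visit L days later, and scheduled visits on Days 43, 99 and 183.
- Overrides at Visits 2, 3 and 4: 204 + 196 + 308 = 708.
- L = 0-14: 708 / (182 x 15) = 708/2730 = 0.259; Week 26 part 308/2730 = 0.113.
- L = 0-7: 708 / (182 x 8) = 708/1456 = 0.486; Week 26 part 308/1456 = 0.212.
- Median gap 19 days, maximum 42.
- Only last-dose Days 7-35, 64-91 and 134-175 can trigger it: 29 + 28 + 42 = 99 of 182.

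These are shares of date combinations, not patient rates. Stops on the day of Visit 1, 2 or 3, for example after the post-dose FEV1 check in Protocol 8.1.2, contribute none. After Visit 1, a discontinuation visit within 7 days comes before Day 14. After Visit 2 or 3, the scheduled value in that slot is itself on-treatment.

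**Plan figures used for scale.** The plan's 350 subjects come from 80 mL, SD 230 mL, 90% power and two-sided 0.05. Check: 2 x (1.960 + 1.282)^2 x 230^2 / 80^2 = 173.7, so 174 per arm or 348 in all, which agrees. For the standard error, 423 subjects were randomized (SAP 10). The re-estimation led to 440, which Table 7 of the protocol assigns to an SD above 249 mL. So SE = 2 x 249 / sqrt(423) = 24.2 mL (22.4 mL at SD 230).

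**Assumptions not in the documents.** A fraction p = 10-30% of the mannitol arm stop drug but stay. The discontinuation value is 80 mL above the scheduled value on mannitol, with no difference on control. The low end pairs p = 10% with L = 0-14; the high end pairs p = 30% with L = 0-7.

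Shift in the equally weighted three-visit mean = p x share x 80 / 3. Shift at Week 26 = p x Week 26 share x 80. Mannitol subjects affected = 211.5 x p x share.

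| Scenario | Share | Three-visit shift | Upper end / SE | Week 26 shift |
|---|---|---|---|---|
| (a) last-dose days spread evenly, full attendance | 0.259-0.486 | 0.7-3.9 mL | 0.16 | 0.9-5.1 mL |
| (b) as (a), 80% independent attendance at each visit (x 0.64) | 0.166-0.311 | 0.4-2.5 mL | 0.10 | 0.6-3.2 mL |
| (c) as (b), half of stops on a clinic day (x 0.5) | 0.083-0.156 | 0.2-1.2 mL | 0.05 | 0.3-1.6 mL |

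For instance, the upper end of (a) is 0.30 x 0.486 x 80 / 3 = 3.9 mL. Affected mannitol subjects run from 211.5 x 0.10 x 0.083 = 2 to 211.5 x 0.30 x 0.486 = 31. With a 0 mL difference the shift is nil. With -40 mL under (a) it is -0.3 to -1.9 mL.

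**The case against.** The rule is prespecified and disclosed in a SAP finalised before unblinding, and 8.1.1 ties the analysis to the Section 6.4 assignment before it speaks of all data. A repeated-measures model with one value per visit cannot use two, so any rule, including the one proposed here, discards something. Later off-treatment visits still enter. All this is true, but it does not reconcile the texts. A choice is unavoidable; making it by treatment status is not, and the second rule in 6.4 shows that a neutral choice was available.

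The size rests on assumed rates and on the full design effect disappearing between the two measurements. That also stands, and it is why the point is graded minor.

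The proposed rule is not always better timed. With last dose on Day 180, a discontinuation visit on Day 183 and Visit 4 on Day 211, the current rule keeps the on-target value. Over all permitted scheduled dates, with the discontinuation visit 0-7 days after the last dose, the discontinuation value is strictly nearer the target in about 8% of override combinations at Visits 2 and 3, and 30% at Visit 4. This is a real but small cost: a scheduled visit inside its protocol window is still a valid treatment-policy value for that visit.

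The protocol gives limited help to either side. Its statistical section names discontinuation-visit data only under sensitivity analysis #2 (10.2.5.2), but the wording there does not confine the data to that analysis. SAP Section 11 does not list their use in the primary analysis as a change.

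**Conclusion.** The inconsistency holds and is minor. Confidence is high on the mismatch between the Section 6.4 rule and the stated estimand, because it rests on the SAP's text alone. Size and direction rest on assumptions. At most one of three visits per subject changes, and no plausible scenario above moves the 26-week contrast by more than about 4 mL. No bias in favour of mannitol is shown. The sample size is unaffected.

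**What to change.** For the primary analysis, Sensitivity Analyses 1-4 and FVC, amend only the first rule under Table 4: where one assessment is on-treatment and the other off-treatment, use the scheduled-visit assessment. Where the scheduled value is the on-treatment one, the present rule already keeps it, so nothing changes. This also fits the opening of 6.4, which bases ITT analyses on the visit recorded in the CRF. Leave the nearest-to-target rule as written, and keep the on-treatment preference for Supportive Analyses 6-8, where it belongs. Report the number of affected values by arm and visit.

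The cost is one amended rule and one derivation flag before unblinding, with no new data. Some retained values will lie further from the target day, and the estimate may move slightly in either direction, including against mannitol.

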## Statistical Analysis Plan

### 6.5. POOLING OF CENTERS

No investigation of center effects is planned, however the stratification factor of country will be included in statistical analysis models as detailed in the following sections. Low numbers of subjects were recruited for at least one country, so countries will be pooled together as United States versus the rest of the world for the stratification factor.

### 6.6. SUBGROUPS

[figure not shown]
Subgroup analyses of primary and hierarchical secondary endpoints will be performed to assess consistency of response between subgroups of subjects:

- With and without rhDNase use.
- With differing disease severity (percent predicted FEV1 at baseline). The following cut point will be used: >70% and ≤70%.

In addition subgroup analyses of the primary endpoint will be performed to assess the consistency of response between subgroups of subjects:

- With and without *Pseudomonas aeruginosa* infection as specified on the sputum qualitative microbiology collected at screening. *Pseudomonas aeruginosa* infection is assumed if there is a recording of mucoid or non-mucoid *Pseudomonas aeruginosa* infection at screening regardless of organism presence or clinical significance. Subjects who did not have a sputum sample analyzed at screening will be excluded from these subgroup summaries and analyses.

All subgroup analyses will be carried out by subsetting the overall population according to the above subgrouping factors and repeating the analysis for each level of the factor. Where applicable (i.e. for rhDNase use and disease severity) the related variable in the analysis model will be dropped.

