10.2.11 Subgroup analyses

Limited subgroup analyses of relevant primary and secondary will be performed to assess consistency of response between those:

- with and without rhDNase use;
- with and without *Pseudomonas aeruginosa* infection;
- with differing baseline percentage of predicted FEV₁.

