## Statistical Analysis Plan

- MMRM with BOCF+IUDR imputation.
- Pattern mixture model.
- MMRM without BOCF.

The primary analysis of absolute change in FEV1 over the 26 week treatment period and the supportive analysis of relative change in FEV1 over the 26 week treatment period will be repeated by the subgroups specified in Section 6.6 on the ITT set only.

The results from the primary analysis, the sensitivity analyses, the supportive analyses, and the subgroup analyses for the primary endpoint will be presented in forest plots to graphically explore the consistency of the estimated treatment effect.

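### SAP 6.6 sets out to assess consistency between subgroups, but no planned analysis estimates the difference in treatment effect between subgroup levels

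*SAP*

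**What the plan says.** The aim appears in both documents. Protocol Section 10.2.11 plans limited subgroup analyses "to assess consistency of response between those" with different baseline features. SAP Section 6.6 repeats it: "Subgroup analyses of primary and hierarchical secondary endpoints will be performed to assess consistency of response between subgroups of subjects".

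The factors are rhDNase use and baseline percent predicted FEV1 cut at 70%. For the primary endpoint there is also *Pseudomonas aeruginosa* infection at screening.

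The method is fixed for all of them. They are "carried out by subsetting the overall population according to the above subgrouping factors and repeating the analysis for each level of the factor". For rhDNase use and disease severity, "the related variable in the analysis model will be dropped".

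SAP Section 8.1 says the primary-endpoint results, subgroups included, will be "presented in forest plots to graphically explore the consistency of the estimated treatment effect". Section 8.2 plans a similar plot for each hierarchical secondary endpoint. The repeated analyses carry their usual outputs: a treatment difference, or a hazard or rate ratio, with 95% CI and p-value (Sections 8.1.1 and 8.2.2 to 8.2.5).

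The only interaction in the primary model is treatment by visit (Section 8.1.1). Table 6 has rows for the MMRM, Cox and negative binomial models by subgroup, but none for an interaction or a between-level contrast.

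**The concern.** Consistency is a statement about the difference between two treatment effects. The plan produces the two effects side by side and stops there, and it gives no criterion for calling them consistent.

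The reader receives many such pairs. FEV1 absolute and relative change over three factors with two levels each give 2 × 3 × 2 = 12 fits. Five hierarchical secondary endpoints over two factors with two levels each give 5 × 2 × 2 = 20. That is 32 separate fits, each with its own p-value and none with a comparison. The easy misreading is to set a significant level against a non-significant one and conclude that mannitol works only in the former.

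There is a second, smaller point. rhDNase use is constant within its own subgroups and has to be dropped. Percent predicted FEV1 does not: it enters the primary model as a continuous covariate (Protocol 10.2.3, SAP 8.1.1) and still varies within the >70% and ≤70% groups. Dropping it means that the severity-subgroup models for FEV1 and FVC no longer match the model they are meant to repeat.

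**Working it through.** **Inputs.** SAP Section 3.5 gives a difference of 80 mL, SD 230 mL, 350 subjects allocated 1:1, two-sided 0.05 and 90% power, based on a Week 26 t-test. The documents give no subgroup shares, so the splits below are assumptions.

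**The plan's own figure.** SE = 2 × 230/√350 = 24.6 mL. Power = Φ(80/24.6 − 1.96) = Φ(1.29) = 90.2%. The stated 90% reproduces.

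**Identical 80 mL effect in both levels.** For a level with share p, SE = 2 × 230/√(350p) and power = Φ(80/SE − 1.96). With powers a and b, the chance that exactly one level is significant is a(1 − b) + b(1 − a).

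| Assumed split | SE by level (mL) | Power by level | Exactly one significant |
|---|---|---|---|
| 50:50 | 34.8 / 34.8 | 63% / 63% | 46% |
| 70:30 | 29.4 / 44.9 | 78% / 43% | 54% |
| 80:20 | 27.5 / 55.0 | 83% / 31% | 63% |

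Setting overall power at exactly 90% instead (power = Φ(3.2415√p − 1.96)) gives 46.6% at 50:50 and 54.0% at 70:30, hence about 47% and 54%.

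**Updated inputs.** SAP Section 10 reports a re-estimated size of 440, with 423 randomized. In Protocol Table 7, 440 corresponds to an SD above 249 mL. With 423 subjects and SD 249 mL, the discordance is 46% (50:50) to 63% (80:20), so the picture does not change.

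**Other yardsticks, same identical effect, 350 subjects, SD 230 mL, splits from 50:50 to 80:20:**
- The larger estimate is at least twice the smaller, or the smaller is at or below zero: 30% to 39% of trials.
- At least one level has a negative estimate: about 2% to 8%.
- The two 95% CIs do not overlap: under 1%.

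**What the missing contrast would show.** The SE of the between-level difference is √(SE_A² + SE_B²).
- 50:50: √(34.8² + 34.8²) = 49.2 mL. The 95% CI half-width is 1.96 × 49.2 ≈ 96 mL. Power for a true 80 mL difference is Φ(80/49.2 − 1.96) = 37%.
- 80:20: √(27.5² + 55.0²) = 61.5 mL. The half-width is about 120 mL and the power is 26%.

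The difference detectable with 80% power is (1.96 + 0.84) × SE, about 138 to 172 mL. When the effects are identical, the interaction test flags a difference about 5% of the time per factor, as it should.

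**The case against.** The strongest reply is that the plan already reports what matters. Each repeated analysis gives an effect estimate with a 95% CI, and the forest plots invite the reader to compare estimates rather than p-values. That stands. A reader might infer that the method yields nothing but within-subset p-values, or that the SAP means to judge consistency by significance. The documents support neither.

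It follows that the 47% and 54% depend on a comparison that the SAP does not prescribe. A reader who looks only for non-overlapping CIs would almost never be misled when the effects are equal. That also stands, although overlap of two CIs is itself a poor substitute for a CI on the difference.

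The subsets within a factor are disjoint, so the contrast and its SE can be recovered from the two reported results. This is true, but it leaves the comparison for readers to compute. It also shows how little the fix costs.

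On the covariate, baseline FEV1 or baseline FVC stays in the model, so the precision lost is probably modest; no figure can be put on it from the documents. The Cox and negative binomial models contain no percent predicted term, so nothing is lost there. Separate fits also avoid assuming a common covariance across levels, which is a defensible choice.

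Finally, the interaction test is weak. That argues for leading with the CI, not for leaving the contrast out.

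**Conclusion.** The gap is real. The stated aim is consistency between subgroups, and no readable part of either document plans an estimate of the between-level difference. Parts of the SAP appendices are redacted, but Section 6.6 states its method for all subgroup analyses.

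If significance is compared across levels, an identical 80 mL effect would look discordant in about 47% of trials at 50:50 and 54% at 70:30. These figures rest on assumed splits, the Week 26 t-test SD and the FEV1 endpoint only. The MMRM averaged over three visits is likely to be more precise (the SAP calls its sizing likely conservative), which would lower them somewhat. The documents give no event rates or dispersion, so nothing comparable can be computed for the exacerbation endpoints.

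A stronger conclusion, that the plan will often declare equal effects inconsistent, does not follow, because no such decision rule is stated. The primary test, its type I error and the testing hierarchy are untouched. What is affected is the interpretation of supportive subgroup results. This is a cheap improvement.

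**What to change.** For each endpoint and factor, fit one model to the ITT set with the subgroup main effect and a treatment-by-subgroup term. For *Pseudomonas*, use the ITT subjects with a screening sputum result, since Section 6.6 excludes the others. In the MMRM add the corresponding by-visit terms, so that the contrast is averaged over visits with equal weights as in the primary analysis.

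Take the level-specific effects from this model. Add to each forest plot the between-level difference (for the Cox and negative binomial models, the ratio of hazard or rate ratios) with its 95% CI and interaction p-value. State in the SAP that the CI carries the interpretation, and that significance within one level and not the other is not evidence of inconsistency.

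In the severity analyses of FEV1 and FVC, keep continuous baseline percent predicted FEV1 in the model.

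The cost is a few lines of SAP text and a little programming on the same data. The downside is a low-power test, which is why the interval should lead. The change belongs in an SAP amendment before unblinding; if made later, it should be labelled as added afterwards.
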